### **11.3 Suspected transmission of an infectious agent**

For the purposes of reporting, any suspected transmission of an infectious agent via a medicinal product should be considered as an SAE; such cases must be reported immediately, recorded in the AE module of the eCRF, and followed as any other SAE. Any organism, virus, or infectious particle (eg, prion protein transmitting transmissible spongiform encephalopathy), pathogenic or nonpathogenic, is considered an infectious agent.

### **11.4 Overdose of investigational medicinal product**

Excessive dosing (beyond that prescribed in the protocol and including overdose) should be recorded in the eCRF. Any SAE or nonserious AE associated with excessive dosing must be followed as any other SAE or nonserious AE. These events are only considered AEs or SAEs if there are associated clinical signs and symptoms or if the act of taking the excess medicine itself is an AE or SAE (eg, suicide attempt).

### **11.5 Safety signal detection**

Selected data from this study will be reviewed periodically to detect, as early as possible, any safety concern(s) related to the IMP so that Investigators, subjects, regulatory authorities, and IRBs/IECs will be informed appropriately and as early as possible.

The Study Physician or medically qualified designee/equivalent will conduct an ongoing review of SAEs and perform ongoing SAE reconciliations in collaboration with the PS representative.

As appropriate for the stage of development and accumulated experience with the IMP, medically qualified personnel at UCB may identify additional safety measures (eg, AEs, vital signs, laboratory, or ECG results) for which data will be periodically reviewed during the course of the study.

In addition, an unblinded independent DMC (Section 13.7) will oversee safety data approximately every 6 months (subject to DMC recommendation) during the course of the study during which the safety of PSL will be assessed. The safety variables and the decision rules to be used will be specified in the DMC Charter. This analysis will inform any decisions regarding changes in study conduct and/or study termination. The precise membership, scope, and responsibilities of the DMC will be described in the DMC Charter.

## 11.6 Laboratory measurements

Laboratory assessments will be conducted using standard methods at a central laboratory. The central laboratory will provide the Investigator with dedicated, standardized sampling equipment (labels, needles, tubes), and a study-specific Laboratory Manual, which will explain how to use the equipment and how to ship the samples to the central laboratory. The laboratory parameters measured are presented in Table 11–2.

The total blood volume drawn for clinical laboratory assessments per subject will be a maximum of 12.1mL by sampling, which includes 3mL for hematology, 4mL for blood chemistry, 5mL for AED plasma level (including back-up samples for AED assay), 20µL for PSL plasma level, and 80µL for PK measurements.

**Table 11–2: Laboratory measurements**

Hematology	Chemistry	Urinalysis
Basophils	ALP	Glucose
Eosinophils	ALT	pH
Hematocrit	AST	RBC
Hemoglobin	Bilirubin	Total protein
Lymphocytes	BUN or urea	WBC
MCH	Calcium	Microscopy (WBC, RBC, casts, crystals, bacteria) a
MCHC	Chloride	Other
MCV	Creatinine	FSH
Monocytes	Glucose	
Neutrophils	HDL	
Platelet count	LDH	
RBC count	LDL	
WBC count	Magnesium	
	Potassium	
	Sodium	
	Total bilirubin	
	Total cholesterol	

ALP=alkaline phosphatase; ALT=alanine aminotransferase; AST=aspartate aminotransferase; BUN=blood urea nitrogen; FSH=follicle stimulating hormone; HDL=high density lipoprotein; LDH=lactate dehydrogenase; LDL=low density lipoprotein; MCH=mean corpuscular hemoglobin; MCHC=mean corpuscular hemoglobin concentration; MCV=mean corpuscular volume; RBC=red blood cell; WBC=white blood cell

a Microscopy will be performed only in case of abnormalities.

Where applicable (ie, for women of childbearing potential), a serum pregnancy test (β-human chorionic gonadotropin levels) will be conducted at Visits 1 and 7 only. A urine pregnancy test

will be used at other visits. If pregnancy is suspected at any time during the study, an interim test should be performed.

Women not agreeing to use birth control must be abstinent or be of nonchildbearing potential, defined as being postmenopausal (for at least 2 years before the Screening Visit [Visit 1]), verified by serum follicle stimulating hormone level  $>40\text{mIU/mL}$  at the Screening Visit (Visit 1) and Visit 7, permanently sterilized (eg, bilateral tubal occlusion, hysterectomy, bilateral salpingectomy), or congenitally sterile (see also Section 6.1).

Sampling time and last AED intake should be recorded in the eCRF.

### 11.6.1 Evaluation of PDILI

The PDILI IMP discontinuation criteria for this study are provided in Section 6.3.1, with the accompanying required follow-up investigation and monitoring detailed below. All PDILI events must be reported as AEs and reported to the study site and Sponsor within 24 hours of learning of their occurrence. Any PDILI event that meets the criterion for potential Hy's Law must be reported as an AE of special interest (see Section 11.1.1.3), and, if applicable, also reported as an SAE (see Section 11.1.1.2).

Evaluation of PDILI consists of the diagnostic testing and continued monitoring included in Table 11-3 (specific tests dependent on laboratory results and corresponding symptoms) and consultation with a local hepatologist (if applicable; discussed in Section 11.6.1.1). The local hepatologist is the expert usually consulted by the treating physician for assessment and management of potential hepatic disease. This would usually be a hepatologist, but may be a gastroenterologist. Additional investigation and monitoring may be required and adapted based on the diagnosis after the cause of the liver injury/abnormality is confirmed (details in Section 11.6.1.4).

The results of all monitoring, including laboratory testing and other testing, should be made available to the study site and Sponsor.

All initial tests resulting in abnormal hepatic laboratory values need to be repeated, but appropriate medical action must not be delayed waiting for the repeat result.

If tests are done locally for more rapid results, a concurrent sample should also be sent to the central laboratory whenever possible. Medical care decisions are to be made initially using the most rapidly available results and a conservative approach must be taken if the results from the 2 laboratory tests are significantly different. Data from the local and central laboratory are to be recorded on the applicable eCRF pages.

When IMP is discontinued, all concomitant medications and herbal supplements that are not medically necessary should also be discontinued. In these cases, the Investigator should also consider dose reduction for medically necessary concomitant medication and consider changing any medically required concomitant medication known to be hepatotoxic to a suitable alternative.

When IMP is stopped due to PDILI (as described in Section 6.3.1), IMP must be permanently discontinued unless a subsequent alternative diagnosis fully explains the hepatic findings. If a subsequent alternative diagnosis fully explains the hepatic findings, and the requirements provided in Section 11.6.1.2.1 are met, rechallenge with IMP may be appropriate.

---

Rechallenge with a substance potentially causing drug-induced liver injury is dangerous, may be fatal, and must not occur.

The approach to investigate PDILI is summarized in [Table 11-3](#).

This document cannot be used to support any marketing authorization application and any extensions or variations thereof.

REDACTED COPY

**Table 11-3: Required investigations and follow up for PDILI**

Laboratory value			Immediate		Follow up	
ALT or AST	Total bilirubin	Symptoms a of hepatitis or hypersensitivity	Consultation requirements	Actions	Testing	Evaluation
≥3xULN	≥2xULN b	NA	Hepatology consult. c	Immediate, permanent IMP discontinuation.	Essential: Must have repeat liver chemistry values and additional testing completed ASAP (see Section 11.6.1.3); recommended to occur at the site with HCP.	Monitoring of liver chemistry values at least twice per week until values normalize, stabilize, or return to within baseline values. d
≥8xULN	NA	Medical Monitor must be notified within 24 hours (eg, by laboratory alert) and subject discussed with Medical Monitor ASAP.	Immediate, temporary or permanent, IMP discontinuation.			
≥3xULN	NA	Yes				
≥3xULN (and ≥2x baseline) and <5xULN	<2xULN	No	Discussion with Medical Monitor required if the criterion that allows for IMP continuation is met.	Further investigation and immediate IMP discontinuation not required (see Section 11.6.1.2).	Not required unless otherwise medically indicated (at discretion of Investigator).	
≥5xULN (and ≥2x baseline)	<2xULN	No	Discussion with Medical Monitor required.	Immediate, permanent IMP discontinuation.	Essential: Every attempt must be made to have repeat liver chemistry values and additional testing completed within 48 hours at the site with HCP (see Section 11.6.1.3).	Monitoring of liver chemistry values at least twice per week until values normalize, stabilize, or return to within baseline values. d

---

ALP=alkaline phosphatase; ALT=alanine aminotransferase; ASAP=as soon as possible; AST=aspartate aminotransferase; HCP=healthcare practitioner; IMP=investigational medicinal product; NA=not applicable; PDILI=potential drug-induced liver injury; ULN=upper limit of normal.

a Hepatitis symptoms include fatigue, nausea, vomiting, and right upper quadrant pain or tenderness; hypersensitivity symptoms include eosinophilia (>5%), rash, and fever (without clear alternative cause).

b If the subject also has  $\geq 2 \times$ ULN ALP, the possibility of an indication of biliary obstruction should be discussed with the Medical Monitor.

c Details provided in Section 11.6.1.1. The local hepatologist is the expert usually consulted by the treating physician for assessment and management of potential hepatic disease. This would usually be a hepatologist, but may be a gastroenterologist.

d Unless an alternative monitoring schedule is agreed by the Investigator and UCB responsible physician. Determination of stabilization is at the discretion of the Investigator in consultation with the hepatologist (as applicable) and UCB responsible physician, as needed.

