### 11.6.1.2 Immediate action: determination of IMP discontinuation

All PDILI events require immediate action, testing, and monitoring.

The immediate action is dependent on the laboratory values and symptoms of hepatitis or hypersensitivity and ranges from continuation of IMP (followed by immediate investigation) to immediate and permanent discontinuation (see Section 6.3.1 and Table 11-3 for details).

When IMP is discontinued, all concomitant medications and herbal supplements that are not medically necessary should also be discontinued. The Investigator should also consider dose reduction for medically necessary concomitant medication and consider changing any medically required concomitant medication known to be hepatotoxic to a suitable alternative.

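### Protocol Table 11-3 says further investigation is not required in the one liver-injury category that may stay on IMP, while Section 11.6.1.2, which the table cites, says continuation is followed by immediate investigation

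*Protocol*

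**What the plan says.** Section 6.3.1 sorts PDILI cases into those that require IMP to stop and one that lets it continue at the Investigator's discretion. The continuing case is ALT or AST at least 3xULN (and at least 2x baseline) and below 5xULN, with total bilirubin below 2xULN and no eosinophilia, fever, rash or hepatitis symptoms. Section 6.3.1 then requires evaluation under Section 11.6.1 to be started, with no exception for this case.

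For this row, Table 11-3 gives:

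- **Consultation:** discussion with the Medical Monitor is required.
- **Actions:** "Further investigation and immediate IMP discontinuation not required (see Section 11.6.1.2").
- **Testing:** not required unless medically indicated, at the Investigator's discretion.

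Section 11.6.1.2, cited in the Actions cell, opens with "All PDILI events require immediate action, testing, and monitoring". It gives a range of immediate actions, the mildest of which is "continuation of IMP (followed by immediate investigation").

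Section 11.6.1 says "All initial tests resulting in abnormal hepatic laboratory values need to be repeated", and adds that medical action must not wait for the repeat result.

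**The concern.** A table cell that names a section as its authority should agree with that section, and this one does not. A site managing a subject who keeps taking IMP with raised transaminases can read in the table that further investigation is not needed, follow the reference, and find that investigation should begin at once. A site that follows either text departs from the other.

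This is the only PDILI category in which exposure may continue, so the instruction on what to investigate matters more here than where the drug has already been stopped. The conflict concerns subject safety and consistency between sites. It does not touch an efficacy endpoint.

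**Working it through.** No arithmetic applies. The check compares the current protocol text on three questions.

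**1. Do the two texts describe the same subjects?** Yes. The Table 11-3 row has the same ALT/AST band, baseline multiple, bilirubin limit and absence of symptoms as the continuing criterion in Section 6.3.1, and its Consultation cell refers to the criterion that allows continuation. Section 6.3.1 has only one such criterion. The parenthesis in Section 11.6.1.2 about continuing IMP therefore has no other category to describe.

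**2. Do they give the same instruction?**

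| Source | Is investigation required when IMP continues? |
|---|---|
| Table 11-3, Actions cell | No, on ordinary grammar: the closing negative governs both items joined by *and* |
| Section 11.6.1.2, general rule | Yes: testing and monitoring for every PDILI event |
| Section 11.6.1.2, on continuing IMP | Yes: immediate investigation follows |
| Section 11.6.1 | Yes, at least a repeat of each abnormal initial test |
| Section 6.3.1 | Yes: evaluation must be initiated |

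**3. Do the cross-references settle it?** They form a loop:

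- Section 6.3.1 sends the site to Section 11.6.1.
- Section 11.6.1 says "Evaluation of PDILI consists of the diagnostic testing and continued monitoring included in Table 11-3", qualified by "specific tests dependent on laboratory results and corresponding symptoms".
- Table 11-3 sends the site to Section 11.6.1.2.
- Section 11.6.1.2 sends it back: "see Section 6.3.1 and Table 11-3 for details".

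The status of the table is also unclear. Section 11.6.1 first makes it the content of the evaluation and later calls it a summary ("The approach to investigate PDILI is summarized in" the table). No sentence says whether table or text prevails.

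**Extent.** One of the five rows of Table 11-3 is affected, and within it the conflict lies in one cell, Actions. The Evaluation cell of this row cannot be read in the text extracted from the PDF, so nothing here rests on it. The documents give no expected number of subjects in this category.

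**The case against.** Four points can be made on the other side.

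*The cell can be read consistently.* It might mean that the action is further investigation, and that immediate discontinuation is not required. That would match Section 11.6.1.2 and would explain the citation. The reading is possible but strained, because the sentence joins both items under one negative. A safety instruction should not need it.

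*The Testing cell is not in conflict.* This stands. A reader might infer that the Testing cell waives the repeat liver chemistry. The documents do not show that. The table's right-hand columns follow the order of Sections 11.6.1.1 to 11.6.1.4, so Testing corresponds most naturally to the search for another cause in Section 11.6.1.3. That section limits the work-up to events with a reasonable possibility of being caused by the IMP, and Section 11.6.1 lets specific tests depend on results and symptoms. Repeat chemistry is a separate, unconditional rule in Section 11.6.1, and nothing in the cell cancels it. Other rows do mention repeat chemistry under Testing, but that does not turn its absence here into a waiver. The cell would benefit from clarification and no more.

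*The safeguards are adequate.* A reader might infer that these subjects go unwatched. They do not. Section 11.6.1.1 requires the Medical Monitor to be notified within 24 hours and the case to be discussed as soon as possible. Section 11.6.1.4 requires follow-up monitoring. Section 6.3.1 stops IMP at once for anyone who cannot keep to the monitoring schedule. This reduces the risk considerably. It does not say whether investigation is required or how far it extends.

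*The analysis is unaffected.* This also stands. SAP Section 10.3.1 counts subjects who meet this band during the Treatment Period, and that count does not depend on a retest.

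**Conclusion.** The point holds for the Actions cell. As worded, it waives further investigation in the only PDILI category that may remain on IMP, and the section it cites says the opposite. This is a wrong instruction in current text rather than a missing detail, and it should be fixed. Its size is one cell in one of five rows, with safeguards elsewhere that keep the practical risk low.

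The conclusion rests on the ordinary grammar of the cell and on the fact that Section 6.3.1 has a single continuing category. It does not depend on the Evaluation cell, on any assumed incidence, or on a view of how much investigation is clinically right. Sections 11.6.1 and 11.6.1.2 do not say whether immediate investigation means repeat chemistry alone or the fuller work-up in Section 11.6.1.3. That is a medical decision for the sponsor.

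**What to change.** - **Actions cell, this row:** replace with *Immediate IMP discontinuation not required; further investigation required (see Section 11.6.1.2)*.
- **Testing cell, this row, as a clarification:** *Repeat liver chemistry per Section 11.6.1; additional Section 11.6.1.3 testing only if medically indicated, as judged by the Investigator*.
- **Scope:** the sponsor's physician should confirm what immediate investigation means for this category.

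If subjects are still being dosed, the cost is two table cells, one medical confirmation and a letter to sites. The SAP (Section 3.9) records early termination. If dosing has ended, amending the table serves no purpose, and one sentence in the study report stating which rule was applied is sufficient. Neither route needs new data or a change to a planned analysis.

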### 11.6.1.1 Consultation with Medical Monitor and local hepatologist

Potential drug-induced liver injury events require notification of the Medical Monitor within 24 hours (eg, by laboratory alert), and the subject must be discussed with the Medical Monitor as soon as possible. If required, the subject must also be discussed with the local hepatologist. The local hepatologist is the expert usually consulted by the treating physician for assessment and management of potential hepatic disease. This would usually be a hepatologist, but may be a gastroenterologist. If determined necessary, this discussion should be followed by a full hepatology assessment (see Section 11.6.1.3) and SAE report (if applicable).

### 11.6.1.2 Immediate action: determination of IMP discontinuation

All PDILI events require immediate action, testing, and monitoring.

The immediate action is dependent on the laboratory values and symptoms of hepatitis or hypersensitivity and ranges from continuation of IMP (followed by immediate investigation) to immediate and permanent discontinuation (see Section 6.3.1 and Table 11-3 for details).

When IMP is discontinued, all concomitant medications and herbal supplements that are not medically necessary should also be discontinued. The Investigator should also consider dose reduction for medically necessary concomitant medication and consider changing any medically required concomitant medication known to be hepatotoxic to a suitable alternative.

#### 11.6.1.2.1 IMP restart/rechallenge

Rechallenge with a substance potentially causing drug-induced liver injury is dangerous, may be fatal, and must not occur.

Subjects who are immediately discontinued from IMP due to having met certain criteria for PDILI (as described in Section 6.3.1 and Table 11-3), but for whom an alternative diagnosis is confirmed, ie, drug-induced liver injury is excluded, can rarely restart IMP. Rechallenge with IMP can occur only if ALL of the following requirements are met:

- The results of additional testing and monitoring described in Section 11.6.1.3 and Section 11.6.1.4 confirm a nondrug-related cause for the abnormal hepatic laboratory parameters and any associated symptoms (ie, a subsequent alternative diagnosis fully explains the hepatic findings).
- No alternative treatment options are available to the subject.
- The subject has shown clear therapeutic benefit from the IMP.
- Subject's ALT or AST elevations do not exceed  $\geq 3xULN$ .
- Subject's total bilirubin is  $< 1.5xULN$ .
- Subject has no signs or symptoms of hypersensitivity.
- The rechallenge is approved by the UCB responsible physician, DMC, and a hepatologist. The hepatologist must be external to UCB but may be a member of the DMC. It is recommended that the hepatologist be a local hepatology expert or the hepatologist treating the subject.
- Subject agrees to the Investigator-recommended monitoring plan and understands their individual benefit/risk for restarting IMP and this is adequately documented.

---

### 11.6.1.3 Testing: identification/exclusion of alternative etiology

The measurements and additional information required for the assessment of PDILI events when there is a reasonable possibility that they may have been caused by the IMP are detailed in [Table 11-4](#) (laboratory measurements) and [Table 11-5](#) (additional information). Results of the laboratory measurements and information collected are to be submitted to the Sponsor on the corresponding eCRF. If the medical history of the subject indicates a requirement for other assessments not included below, these additional assessments should be completed and submitted, as applicable.

All blood samples should be stored, if possible. If tests are done locally for more rapid results, a concurrent sample must also be sent to the central laboratory.

This document cannot be used to support any marketing authorization application and any extensions or variations thereof.

REDACTED COPY

The following measurements are to be assessed:

**Table 11–4: PDILI laboratory measurements**

Virology-related	Hepatitis A IgM antibody
	HBsAg
	Hepatitis E IgM antibody
	HBcAb-IgM
	Hepatitis C RNA
	Cytomegalovirus IgM antibody
	Epstein-Barr viral capsid antigen IgM antibody (if unavailable, obtain heterophile antibody or monospot testing)
Immunology	Anti-nuclear antibody (qualitative and quantitative)
	Anti-smooth muscle antibody (qualitative and quantitative)
	Type 1 anti-liver kidney microsomal antibodies (qualitative and quantitative)
Hematology	Eosinophil count
Urinalysis	Toxicology screen
Chemistry	Amylase
	If total bilirubin $\geq 1.5 \times \text{ULN}$ , obtain fractionated bilirubin to obtain % direct bilirubin
	Serum CPK and LDH to evaluate possible muscle injury causing transaminase elevation
Additional	Prothrombin time/INR a
	Serum pregnancy test
	PK sample

ALT=alanine aminotransferase; CPK=creatine phosphokinase; HBcAb-IgM=hepatitis B core antibody-IgM; HBsAg=hepatitis B surface antigen; IgM=immunoglobulin M; INR=international normalized ratio; LDH=lactate dehydrogenase; PDILI=potential drug-induced liver injury; PK=pharmacokinetic; RNA=ribonucleic acid; ULN=upper limit of normal

a Measured only for subjects with ALT  $> 8 \times \text{ULN}$ , elevations in total bilirubin, and symptoms of hepatitis or hypersensitivity. Hepatitis symptoms include fatigue, nausea, vomiting, and right upper quadrant pain or tenderness; hypersensitivity symptoms include eosinophilia ( $> 5\%$ ), rash, and fever (without clear alternative cause).

The following additional information is to be collected:

